### **8.1.3 Month 1 ( $\pm$ 7 days), Follow-up visit and End of Study Visit for powder BoNT-A treatment group, Visit 3**

The Investigator or designee will:

1. Ask the subject about Aes using an open-ended question, such as "*Have you noticed any change in your health since the last visit?*" Record all Aes as appropriate (Section 7.2.1).
2. Ask the subject about any changes in his/her concomitant therapies/procedures (added, removed or changed) since the previous visit. Record changes in concomitant therapies/procedures as appropriate (Section 5.4).
3. Take subject photographs (see Section 7.3.1).
4. For powder BoNT-A treated subjects:
  - Exit the subject from the study.
5. For Alluzience treatment group subjects:

GALDERMA EST. 1981	Title 05PF2005 Clinical Study Protocol - STAR	Doc id MA-48441
-----------------------	---	---------------------------

CCI

- Schedule the next visit (Month 2  $\pm$ 7 days).

CCI

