## SCHEDULE OF ASSESSMENTS

**Table 2 Schedule of Assessments**

1 month = 4 weeks/28 days Visit windows are calculated from Baseline/Visit 2 if not otherwise specified.	Visit 1 Group 1 and 2	Visit 2 Group 1 and 2	Visit 3/ Group 1 EoS Group 2	Visit 4 Group 1	Visit 5 Group 1	Visit 6/ET EoS Group 1
	Screening 	Treatment/ Baseline  (within 3 weeks after screening)	1-Month Follow-up (±7 days)	3-Month Follow-up (±7 days)	5-Month Follow-up (±7 days)	6-Month Follow-up (±7 days)
Informed Consent	X	(X) 				
Demographic Data including, medical history & con-current diseases, previous facial treatments/ procedures	X	(X) 				
Inclusion /Exclusion Criteria	X	X				
Adverse Events 		X	X	X	X	X
Concomitant Medication/ Procedures	X	X	X	X	X	X
Urine Pregnancy Test 	X	X				
Photography		X	X	X		X
Randomization		X				
Treatment		X				
End of study 			X Group 2, powder BoNT-A			X Group 1, Alluzience
Investigator Assessments						
Reconstitution/Preparation Questionnaire		X				
Investigator Treatment Session Questionnaire 		X				
CCI						

1. Screening and treatment/baseline visits can be performed at the same day
2. Only to be conducted if no screening visit has been performed. Changes to medical history should be asked for if the screening and baseline visits are not performed on the same day.
3. AEs are collected from treatment to the end of the subject's participation, for details how to follow-up ongoing AEs at the last visit see section [7.2.1.1.5](#).
4. Only for women of childbearing potential
5. Subjects in the powder BoNT-A treatment group will be followed 1 month and subjects in the Alluzience treatment group will be followed for 6months.
6. Only for Alluzience-treated subjects
7. Only to be completed once for each Treating Investigator, per study product, after all enrolled subjects have completed Visit 2.
8. Performed pre-treatment

CONFIDENTIAL

Page 17 of 71

*Effective*

GALDERMA EST. 1981	Title 05PF2005 Clinical Study Protocol - STAR	Doc id MA-48441
-----------------------	---	---------------------------

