11. Ask the subject about any Aes experienced, in connection to, and after the treatment. Record Aes, as appropriate, on the corresponding eCRF form(s).
12. Record post-treatment concomitant therapies/procedures.
13. Ask the subject to complete the Subject Treatment Session Questionnaire (Appendix 4).
14. Complete the Reconstitution/Preparation Questionnaire (Appendix 1) and the Investigator Treatment Session Questionnaire (Appendix 2).
15. Schedule the next visit (Month 1  $\pm$ 7 days).

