#### **8.1.4 Month 3, 5 and 6 ( $\pm$ 7 days), Follow-up visits and End of Study Visit/Early Termination Visit for Alluzience treatment group, Visit 4, 5 and 6**

The Investigator or designee will:

1. Ask the subject about Aes using an open-ended question, such as "Have you noticed any change in your health since the last visit?" Record all Aes as appropriate (Section 7.2.1).
2. Ask the subject about any changes in his/her concomitant therapies/procedures (added, removed or changed) since the previous visit. Record changes in concomitant therapies/procedures as appropriate (Section 5.4).
3. Take subject photographs (see Section 7.3.1) (only visit 4 and 6).

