4. CCI
- 5.
6. Schedule the next visit Month 5 ( $\pm$ 7 days), OR Month 6 ( $\pm$ 7 days), OR complete the end of study form at visit month 6 (Visit 6), depending on current visit.
7. Exit the subject from the study.

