4.1 Trial Periods

4.1.1 Alluzience Group

The study consists of six visits for the Alluzience group: screening (Visit 1), treatment (Baseline/Visit 2) and four follow-up visits at 1 (Visit 3), 3 (Visit 4), 5 (Visit 5) and 6 (Visit 6) months after treatment. The screening visit and the treatment visit might be conducted at the same day.

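### Protocol 8.1.3 books the visit after Month 1 at Month 2 (Days 49–63) for Alluzience subjects, but every visit schedule puts it at Month 3 (Days 77–91); the passages must be reconciled

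*Protocol*

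**What the plan says.** Protocol 8.1.3 describes Visit 3. Powder BoNT-A subjects leave the study there; for Alluzience subjects, step 5 reads "Schedule the next visit (Month 2", with a window of 7 days either side.

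The schedules say something else about the visit that follows Visit 3:

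- Protocol Table 2, in the Visit 4 column: "3-Month Follow-up (±7 days". SAP Appendix A reproduces this table.
- Protocol 8.1.4, in its heading: "8.1.4 Month 3, 5 and 6", "for Alluzience treatment group, Visit 4, 5 and 6".
- SAP 4.1.1: "four follow-up visits at 1 (Visit 3), 3 (Visit 4), 5 (Visit 5) and 6 (Visit 6) months after treatment".
- The protocol synopsis, Table 1 and section 3 give follow-up at Months 1, 3, 5 and 6, without visit numbers.

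The other two scheduling steps are Protocol 8.1.2 step 15, "Schedule the next visit (Month 1", and Protocol 8.1.4 step 6, "Schedule the next visit Month 5" (or Month 6, depending on the current visit). The Table 2 header fixes the anchor: "Visit windows are calculated from Baseline/Visit 2 if not otherwise specified". It also sets one month at 28 days.

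**The concern.** Step 5 is an instruction that sites act on, not background text. It is also the only visible step that books Visit 4, because 8.1.4 step 6 books only Months 5 and 6. A site that follows it as written has two possible outcomes:

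- The visit is entered as Visit 4. It is then out of window against Table 2, which is a named deviation type in SAP 7.5, with its duration reported under SAP 7.5.1. SAP 4.2 tabulates data under the visit recorded on the eCRF, so whatever is collected would be reported as Visit 4 data.
- The visit is held in addition to Visit 4. The subject then makes a visit that no schedule provides for.

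The data exposed are the Visit 4 photographs (Protocol 7.3.1) and any Visit 4 assessments that are redacted in the public text.

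**Working it through.** **Inputs**

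| Input | Value | Source |
|---|---|---|
| Length of a month | 28 days | Protocol Table 2 header; Protocol 5.2 |
| Anchor | Baseline = Day 0 | Protocol Table 2 header; heading of 8.1.2 |
| Window | ±7 days | Protocol 8.1.3 step 5; Table 2 |
| Subjects per site | about 10 to 20 | Protocol 5.1 |
| Group sizes | 100 Alluzience, 50 powder BoNT-A | Protocol 5.1 |

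**Windows** (target = months × 28; window = target ± 7)

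- Month 2: 2 × 28 = 56, so Days 49–63 (15 possible days).
- Month 3: 3 × 28 = 84, so Days 77–91.

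There is no overlap. The SAP's relative study day adds 1 (SAP 4.2), which gives Days 50–64 and 78–92 with the same separation. The result does not depend on the 28-day convention: with 30-day months the windows are Days 53–67 and 83–97, still apart.

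**How early a step 5 visit would be, measured against the Table 2 Visit 4 window**

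- Before the window opens: 77 − 63 = 14 to 77 − 49 = 28 days.
- Before the target day: 84 − 63 = 21 to 84 − 49 = 35 days.

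**How SAP 7.5.1 would report it.** That section refers both to the window date range and to the target date, so the band depends on the reading.

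- From the target date: 21–35 days early, so all 15 days fall in the band of 21 days or more.
- From the window edge: Days 49–56 are 28 to 21 days early (8 of 15, band of 21 or more); Days 57–63 are 20 to 14 days early (7 of 15, band of 8–20).

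The visit is out of window under both.

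**Subjects affected at a site that follows step 5**

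- 10 × 100/150 = 6.7
- 20 × 100/150 = 13.3

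That is about 7 to 13 Alluzience subjects per site.

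**Could Month 2 be an interval from Visit 3?** Two months after Month 1 would be 28 + 56 = Day 84, the Visit 4 target. The text weighs against this reading. Table 2 counts from baseline unless stated otherwise, and step 5 states nothing else. The scheduling steps in 8.1.2 and 8.1.4 name the month from baseline, so step 5 would be the only one written as an interval.

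**Could another source explain it?** The only other two-month entries are in Protocol Tables 3 and 4, which report earlier trials. The summary of changes does not mention the item, and step 5 is current Version 5.0 text.

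**The case against.** The strongest case is that this is one odd number in one bullet and the documents largely contain it. Protocol 8.1 refers sites to Table 2, the next section is headed with Months 3, 5 and 6, and no visible section describes procedures for a Month 2 visit. If an extra visit were held and recorded as unscheduled (Protocol 8.2), SAP 4.2 would confine its questionnaire scores to listings. No visible endpoint or SAP analysis uses the Visit 4 photographs. All of this stands, and it limits the consequence. It does not remove the contradiction from an operative step.

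Three narrower points also have some force:

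- Redactions sit next to step 5, so the absence of a Month 2 visit elsewhere is established for visible text only. The visible schedules nevertheless set out exactly four follow-up visits.
- The passages that agree with each other are not all independent. The synopsis and section 3 share a sentence, and Table 2 and SAP Appendix A are the same table.
- In SAP 7.5.1, counting from the target date would leave the bands up to 7 days empty for out-of-window follow-up visits, since such a visit is by definition more than 7 days off target. That favours the window-edge reading, but the visit is a deviation under either.

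**Conclusion.** The inconsistency is real. Protocol 8.1.3 step 5 and the visit schedules give windows 14 days apart at their nearest edges, and one visit cannot meet both. A visit booked under step 5 would be 14–28 days before the Table 2 window opens.

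The consequence is limited. The primary endpoint and the visible secondary endpoints are collected at Visit 2. Adverse events and concomitant therapies are collected throughout and, in the visible SAP, are not summarised by visit. No effect on any efficacy estimate is claimed, because the Visit 4 assessments are partly redacted.

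Exposure runs from zero, if every site works from Table 2, to about 7–13 Alluzience subjects at each site that follows step 5. The per-site figure assumes that the overall 100:50 split holds within site.

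**What to change.** Reconcile Protocol 8.1.3 step 5 with the synopsis, Table 1, Table 2, section 3 and 8.1.4 of the protocol, and with SAP 4.1.1 and Appendix A, so that one visit schedule applies throughout. Notify the sites. The sponsor must decide which timing is intended; this review does not.

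If the schedule shared by the other passages stands, the cost is one line of protocol text and a site note, with no change to the SAP, the data collected or the analysis sets. SAP 7.5 and 7.5.1 already list and summarise any out-of-window visits that have occurred. If the Month 2 instruction were kept instead, the schedules in both documents would need editing as well.

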#### **8.1.4 Month 3, 5 and 6 ( $\pm$ 7 days), Follow-up visits and End of Study Visit/Early Termination Visit for Alluzience treatment group, Visit 4, 5 and 6**

The Investigator or designee will:

1. Ask the subject about Aes using an open-ended question, such as "Have you noticed any change in your health since the last visit?" Record all Aes as appropriate (Section 7.2.1).
2. Ask the subject about any changes in his/her concomitant therapies/procedures (added, removed or changed) since the previous visit. Record changes in concomitant therapies/procedures as appropriate (Section 5.4).
3. Take subject photographs (see Section 7.3.1) (only visit 4 and 6).
4. CCI
- 5.
6. Schedule the next visit Month 5 ( $\pm$ 7 days), OR Month 6 ( $\pm$ 7 days), OR complete the end of study form at visit month 6 (Visit 6), depending on current visit.
7. Exit the subject from the study.

#### **8.2 Unscheduled Visits**

When necessary, unscheduled visits may be conducted, in particular if an AE occurs and needs to be assessed and/or treated.

#### **8.3 Subject Instructions**

Subjects will be advised that any facial make-up will need to be removed before taking the study photographs.

 EST. 1981	Title 05PF2005 Clinical Study Protocol - STAR	Doc id MA-48441
---	--	----------------------------------

## 9. STATISTICAL METHODS PLANNED

### 9.1 Statistical and Analytical Plans

A Statistical Analysis Plan (SAP) will be developed as a separate document. The SAP will contain a detailed and technical description regarding specific data conventions, calculations and the statistical procedures that will be used to perform the analyses that are specified in the sections below. The SAP will be finalized prior to database lock.

Any changes made to the finalized SAP will be documented in the Clinical Study Report.

#### 9.1.1 Populations Analyzed and Evaluability

The statistical analyses will be performed based on the following subject populations.

##### 9.1.1.1 *Full Analysis Set (FAS) Efficacy Population*

The FAS includes all randomized and treated subjects. FAS will be used for all efficacy evaluations.

##### 9.1.1.2 *Per-protocol (PP) Efficacy Population*

The Per Protocol (PP) population is a subset of the subjects in the FAS population who complete the Month 1 visit and have no protocol deviations considered to have a substantial impact on the primary efficacy outcome. The primary efficacy endpoint will be evaluated using the PP population if the PP population consists of less than 95% of the FAS population.

##### 9.1.1.3 *Safety Population*

The safety population includes all subjects who were administered study product (i.e., Alluzience or powder BoNT-A). Safety analysis will be performed based on the Safety population.

##### 9.1.1.4 *Imputation of Missing Data*

No imputation of missing data will be performed, i.e. analyzes will be performed on observed cases (OC). The number of missing values will be summarized and reported as appropriate.

### 9.1.2 Data Presentation and Graphics

All statistical analyses, including summary tables and data listings, will be performed using the SAS® system (Version 9.4 or higher).

All efficacy, safety and baseline characteristics variables will be presented using descriptive statistics within each treatment group, and graphs as appropriate. Continuous data will be summarized using n (number of observations), mean, standard deviation, median, minimum and

CONFIDENTIAL

Page 51 of 71

 EST. 1981	Title 05PF2005 Clinical Study Protocol - STAR	Doc id MA-48441
---	--	----------------------------------

maximum value, while categorical data will be presented by n and percentages. All data will also be listed in subject data listings.

Subject disposition, completion and discontinuation by study visit, protocol deviations, demographics and baseline characteristics, medical history, medical and surgical procedures, and prior and concomitant medications will be summarized by treatment group.

#### **9.1.2.1      *Subgroup Analysis***

No subgroup analyzes will be performed.

#### **9.1.2.2      *Safety Analysis***

Adverse Events (AE) will be summarized by number of subjects and number of events per treatment group. Aes will be summarized by causality, system organ class , preferred term and maximum intensity. All related Aes will also be summarized by time to onset, duration and action taken.

Aes occurring before treatment will only be provided in subject data listings.

#### **9.1.2.3      *Efficacy Analysis***

All efficacy analysis will be performed descriptively by treatment group (if applicable).

The Investigator Treatment Session Questionnaire, **CCI**

will be presented by category and also by using three categories (Strongly agree/Agree, Neither agree nor disagree, and Disagree/Strongly disagree).

**CCI**

**CCI**

#### **9.1.3      *Withdrawals and Deviations***

All withdrawn subjects will be listed individually, including at least subject number, date and reason for withdrawal, and last visit performed.

Subjects with CSP deviations will be listed individually, including subject number and observed deviation. They will also be summarized in total (by treatment group and overall) as well as by study site. Depending on the seriousness of the deviation, the subject might be excluded from the PP population, which shall be documented prior to database lock.

GALDERMA EST. 1981	Title 05PF2005 Clinical Study Protocol - STAR	Doc id MA-48441
-----------------------	---	---------------------------

#### **9.1.4 Inferential Statistical Analyses**

No inferential statistics will be performed.

#### **9.2 Sample Size Determination**

The sample size of approximately 150 subjects, 100 subjects in the Alluzience treatment group and 50 in the powder BoNT-A treatment group, is not based on a statistical calculation. The selected number of subjects is regarded as sufficient for an evaluation of the studied endpoints by using descriptive statistics.

#### **9.2.1 Interim Analysis**

No interim analysis will be performed.

### **10. TRAINING / MONITORING / DATA MANAGEMENT / QUALITY ASSURANCE**

#### **10.1 Personnel Training**

Investigators and other responsible persons should be listed together with their function on the signature and delegation log. Study staff shall provide a curriculum vitae or equivalent, as appropriate.

It is the responsibility of the Principal Investigator (PI) to ensure that all personnel involved in the study are fully informed regarding all relevant aspects of the study, including detailed knowledge of and documented training in all procedures to be followed.

#### **10.2 Clinical Monitoring**

The conduct of the clinical study will be closely monitored by representatives of the Sponsor to verify that the rights and well-being of the subjects are protected; the reported data are accurate, complete, and verifiable from source documents; and to verify adherence to the CSP, ICH GCP guidelines, national regulations, and applicable SOPs.

The Investigator will allow the CRO/Sponsor representatives to have direct access to all clinical study records, case report forms (CRFs), corresponding subject medical records, study products, dispensing records, and any other documents considered as source documentation. Additionally, the CRO/Sponsor representative is to have access to the study product storage area and clinical study facilities. The Investigator also agrees to assist the CRO/Sponsor representative when required.

CSP deviations shall be reported, verified by the monitor, and appropriate corrective and preventive actions shall be taken. The PI is responsible for promptly reporting any deviations from the CSP that affects the rights, safety or well-being of the subject or the scientific integrity of the study, including

GALDERMA EST. 1981	Title 05PF2005 Clinical Study Protocol - STAR	Doc id MA-48441
-----------------------	---	---------------------------

Effective date: 2021-12-01 17:39

Effective

Version: 5.0

those which occur under emergency circumstances, to the Sponsor as well as the IEC if required by national regulations. Deviations shall be reviewed to determine the need to amend the CSP or to terminate the study. Handling of CSP deviations shall be performed as described in the monitoring manual.

### 10.3 Data Management

Data management based on GCP refers to the activities that ensure secure and robust routines for efficiently entering clinical data into a database. The data management routines include procedures for database set-up and management, data entry and verification, data validation, and documentation of the performed activities and any discrepancies in the process. The data management process will be described in detail in the Data Management Plan (DMP).

The database and data entry screens will be designed in accordance with CSP and eCRF specifications. The EDC system is compliant with regulatory requirements for software validation. Data validation will be performed by computerized logical checks and manual review. Drugs and events will be coded in accordance with the World Health Organization (WHO) Drug database and the Medical Dictionary for Regulatory Activities (MedDRA) as specified in the DMP. Safety data (SAE, and if applicable, AEs of special interest) in the clinical database will be reconciled against the data in the safety database.

When all efforts have been made to ensure that the data recorded in the eCRFs and entered into the database are as correct and complete as possible, the clinical database will be locked. Study data will be transferred to SAS datasets, which thereafter will be write-protected. Statistical analyses will be generated in SAS using data from the locked datasets.

### 10.4 Quality Assurance/Audit/Inspection

The clinical study is conducted under the sponsorship of the Sponsor in compliance with the applicable international and local regulatory requirements as well as applicable ICH guidelines and in accordance with the SOPs for clinical study conduct and monitoring from the Sponsor and/or CRO.

Audits of clinical study sites may be conducted by the CRO/Sponsor representatives, and inspection may be performed by RA inspectorates or an IEC before, during or after the clinical study. For audits performed by or on behalf of the Sponsor, audit certificate(s) will be provided by Quality Assurance.

The Investigator will allow and assist the CRO/Sponsor representatives, IEC and regulatory agencies to have direct access to all requested clinical study-related records.

GALDERMA <small>EST. 1981</small>	Title 05PF2005 Clinical Study Protocol - STAR	Doc id MA-48441
--------------------------------------	---	---------------------------

## 10.5 Changes in Clinical Study Conduct/Amendments

### 10.5.1 Clinical Study Conduct

With the exception of eliminating an immediate hazard to a subject, the Investigator should not deviate from the CSP or implement any changes without written approval from the Sponsor and prior review and documented approval/favorable opinion from the IEC of a protocol amendment.

Changes that involve only logistical or administrative changes to the CSP are authorized. The Investigator should document and explain any deviation from the CSP.

### 10.5.2 Amendments

The Sponsor may modify the CSP at any time for ethical, medical, or scientific reasons. Any amendments will be handled according to applicable local regulations.

The Sponsor does not have to notify non-substantial amendments to the competent authorities or IECs. However, non-substantial amendments should be recorded and detailed in subsequent submissions, e.g., in the subsequent notification of a substantial amendment.

## 11. ETHICS AND GENERAL CLINICAL STUDY CONDUCT CONSIDERATIONS

### 11.1 Independent Ethics Committee (IEC) and Regulatory Authorities (RA)

This CSP and all applicable amendments will be reviewed and approved by the appropriate IEC. It is the responsibility of the PI to obtain approval of the CSP/CSP amendment(s) from the IEC. The study shall not begin until the required favorable opinion from the IEC has been obtained. The PI shall file all correspondence with the IEC in the Investigator file and provide copies of IEC approvals to the Sponsor as required. Any additional requirements imposed by the IEC or RA shall be followed.

This study requires application for approval from the RA. The study will not be started until the Sponsor has received written approval or until the statutory waiting period from the appropriate authority has elapsed. The Sponsor will provide the PI with a copy of the relevant RA approval documentation.

The collection, access to, processing, and transfer of protected health information or sensitive personal data shall be carried out in accordance with applicable rules and regulations.

GALDERMA EST. 1981	Title 05PF2005 Clinical Study Protocol - STAR	Doc id MA-48441
-----------------------	---	---------------------------

